#### **5.36 Quality monitoring of the treatment**

There is no requirement for intravascular thrombectomy devices in this study, and devices that have been approved by the State Food and Drug

Administration of China devices approved by the State Food and Drug Administration of China can be used. Stenting is the preferred method in this study; if unsuccessful, suction devices may be used as a second-line option. The decision to use a combination thrombolytic strategy such as alteplase was left to the discretion of the treating physician based on the intraoperative situation, and the reasons for this were requested.

Control of surgical and pharmacologic bias: Patients undergoing an EVT procedure should have the first device (stent or aspiration catheter) used documented. The target time from imaging to decision grouping is less than 30 min; the target time from imaging to arterial pathway creation or puncture is less than 60 min; and the target time from imaging to revascularization is less than 120 min. Optimal treatment is given in the perioperative period or with drug therapy alone.

### **5.37 Outcomes**

The primary outcome was the modified Rankin Scale score (mRS 90d) of a randomized group of modified intention-to-treat (mITT) patients (defined as patients with acute macrovascular occlusions treated optimally with endovascular or pharmacologic therapy) at 90 days (with an assessment time window of  $\pm 14$  days) and analyzed for noninferiority. If the primary analysis indicated possible superiority, superiority was tested as a secondary objective. Data were collected by structured interviews (telephone interviews) with patients using a standardized form by trained physicians who were unaware of the subgroup results. A standardized written report of each interview was presented to two members of the outcome committee, who confirmed the scores and reached agreement.

The secondary outcomes were as follows:

Proportion of patients in each group receiving interventions Good prognosis for patients receiving interventions

- 1) Patient death within 90 days.
- 2) Successful reperfusion after embolization, defined as an extended Thrombolysis in Cerebral Infarction (eTICI) score of 2b, 2c or 3 at the time of the first intracranial angiogram.
- 3) Percentage of patients revascularized 24 to 72 hours after surgery (as determined by CTA).
- 4) NIHSS scores at 24 hours and 5 to 7 days postoperatively (or at discharge).
- 5) Final infarct volume (calculated by CBV or DWI) at 24 hours and 5 to 7 days postoperatively (or at discharge).
- 6) Comparison of modified Rankin scores at 90 days (0 or 1 vs. 2-6; 0-2 vs. 3-6; 0-3 vs. 4-6; 0-4 vs. 5 or 6; and 0-5 vs 6).
- 7) Quality of life assessment at 90 days: European Five Dimensions and Five Levels Scale (EQ-5D-5L) scores (range, -0.39 [worst] to 1.00 [best]); Barthel

Index scores at 90 days (range, 0 [severe disability] to 100 [no disability]).

Safety outcomes: included all hemorrhage and symptomatic intracranial hemorrhage (Judged by the Heidelberg Classification of Hemorrhage); intraoperative arterial puncture site pseudoaneurysm and inguinal hematoma, cerebral infarction in an additional vascular area at 5 to 7 days, and death within 90 days. The timing of clinical evaluation included at baseline, 24 hours after randomization, 5 to 7 days, or at discharge, whichever occurred first, and 90 days (with an assessment time window of  $\pm 14$  days).

All clinical evaluators should receive on-site and web-based video training on how to perform clinical evaluations. Imaging results are evaluated in a separate imaging core laboratory by trained personnel who are unaware of the subgroup results. All images were reviewed by two individuals and disagreements were reached. We used F-Stroke software for the final automated analysis of infarct lesion volumes.

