### 5.33 Study Implementation Process

Patient enrollment methods:

- A) Emergency greenway triage based on signs and symptoms and NCCT: In this study, a team of emergency department neurologists screened patients for possible large vessel occlusion at 6-24 hours of onset based on head CT scan and NIHSS score  $\geq 6$  and RACE score  $\geq 5$  as proposed subjects.
- B) Clearly diagnosed acute large vessel occlusion (ELVO)

Patients who have performed one of the MRI plain or perfusion examinations but do not meet the inclusion criteria for the DAWN or DEFUSE3 studies may be considered for inclusion. After enrollment, the appropriate imaging modality was selected according to the group as the basis for whether or not to perform interventional treatment.

Screening may be included in cases where either MRI or perfusion imaging is available at the time of the stroke specialist's evaluation of the patient, but the patient or authorized delegated family member is temporarily unable to decide whether to undergo the procedure, or under special irresistible conditions such as occupancy of the interventional suite.

Patients who met the entry criteria were then randomized 1:1 by the arriving stroke specialist into two groups 1 and 2 as follows, with the order of randomization being the responsibility of an independent investigator.

1. The MRI group performed DWI, FLAIRE, T1, T2 and MRA sequences.
2. The Control group underwent MRA or CTA, perfusion sequences, and F-stroke software (Brain Seal Smart Technology).

After randomization, the attending interventionalist decided the treatment based on the history and imaging data of the respective group. All patients were treated with the standard embolization procedure and or the optimal drug therapy. The primary outcome was the overall distribution of **MITT** patients' modified Rankin Scale scores at 90 days postoperatively in both groups, as assessed by the corrected co-ratio. Multiple secondary outcomes, including death, symptomatic intracranial hemorrhage, and

ischemic regional reperfusion, and safety outcomes were also assessed for the included study population.

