#### **5.34 Statistical methods**

The primary efficacy analyses were performed by shift analysis, applying cumulative ordinal logistic regression to estimate the common OR and to evaluate the improvement in mRS scores in the **mITT** population. For secondary efficacy and safety analyses, statistical significance of differences between groups was assessed by Pearson  $\chi^2$  test or Fisher exact test for categorical variables, and by t test or Mann-Whitney test for continuous variables and safety endpoints for all patients. Descriptive analyses of adverse events were presented in the form of totals and events. Multivariate logistic or ordinal regression analyses were applied to determine independent estimators of good functional outcomes and were expressed as OR values and their 95% confidence intervals (95% CI). Two-sided values of  $P < 0.05$  were considered statistically significant. All statistical analyses were performed with IBM SPSS Statistics for Windows, version 19 (IBM Corp).

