#### **5.35 Evaluation criteria for embolization procedures**

MRI group: patient meets the criteria for entry; MRA meets the criteria for large vessel occlusion; and one of the following criteria is met: 1) presence of FVH-DWI mismatch sign (see Appendix) and infarct volume  $< 70$  ml; 2) inability to obtain FLAIR sequence or to determine whether there is a FVH-DWI mismatch using the following criteria: patients  $\geq 80$  years old, preoperative NIHSS  $\geq 6$  points, DWI infarct volume  $< 21$  ml, 2) patients  $< 80$  years old, preoperative NIHSS  $\geq 6$  points, DWI infarct volume  $< 31$  ml, 3) patients  $< 80$  years old, preoperative NIHSS  $\geq 6$  points, DWI infarct volume  $< 31$  ml 3) patients  $< 80$  years old with preoperative NIHSS  $\geq 20$  and DWI infarct volume less than 51 ml (see Appendix [9] for infarct volume evaluation methods); 3) patients with other conditions where MRI infarct volume cannot be determined, where MRI has failed, or where patients with atypical posterior circulation stroke are included are judged by operator experience as to whether to perform surgical treatment; Control group. Patients met the inclusion criteria; MRA/CTA was consistent with large vessel occlusion; preoperative NIHSS  $\geq 6$ ; F-Stroke (CBV  $< 70$  mL; mismatch ratio  $\geq 1.8$ ; mismatch volume  $> 15$  ml). CTA and CT perfusion were preferred in the Control group. The above results were evaluated by two neurointerventional specialists based on the readings provided by the respective groups, and the decision to perform the procedure was made by a third senior neurointerventional specialist in case of disagreement.

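### One secondary outcome, good prognosis among patients operated on, is compared between arms in a subset that the allocated imaging strategy selects after randomisation

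*Protocol*

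**What the plan says.** The order of events is set in the protocol, section 5.33. First, "Patients who met the entry criteria were then randomized 1:1 by the arriving stroke specialist into two groups 1 and 2". Then, "After randomization, the attending interventionalist decided the treatment based on the history and imaging data of the respective group".

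Section 5.35 gives each arm its own rule for operating, once large vessel occlusion is shown:

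- MRI arm: "presence of FVH-DWI mismatch sign (see Appendix) and infarct volume" below 70 ml. If the mismatch cannot be judged, limits on age, NIHSS and DWI volume apply. In remaining cases operator experience decides.
- Control arm: "MRA/CTA was consistent with large vessel occlusion; preoperative NIHSS" of at least 6, with perfusion thresholds for core volume (below 70 mL), mismatch ratio (at least 1.8) and mismatch volume (above 15 ml).

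Section 5.37 opens its secondary outcomes with two unnumbered lines, "Proportion of patients in each group receiving interventions" and "Good prognosis for patients receiving interventions". Good prognosis is not defined there. Item 6 of the same list compares 90-day modified Rankin scores at five cut-points, among them 0-2 versus 3-6, without restricting them to operated patients.

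For secondary efficacy analyses, section 5.34 states that "statistical significance of differences between groups was assessed by Pearson" chi-square or Fisher exact test for categorical variables, at two-sided P < 0.05. It exempts no secondary outcome and states no adjustment for selection in these tests.

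**The concern.** Being operated on is a consequence of the strategy under test. A between-arm comparison confined to operated patients therefore compares two groups that the strategies themselves have put together. Infarct volume, age and NIHSS enter the rules and bear on prognosis, so the two operated groups need not have the same expected outcome even if the procedure works equally well in both.

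The trial asks whether MRI selection is non-inferior to perfusion selection. One way for a strategy to be worse is to withhold the procedure from patients who would have benefited. Those patients drop out of this outcome's denominator, so the failure would not show, or would look like a success. The secondary objective (section 4) is the value of FVH-DWI mismatch in endovascular treatment, and a P value from this item would readily be quoted in support of it.

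**Working it through.** The protocol gives no selection rates, outcome rates, margin or power for its 214 patients, so there is no figure to reproduce. The check has three steps. All rates in steps 2 and 3 are assumptions.

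**1. Is the subset formed after randomisation, and by arm?** Yes. Section 5.33 places the decision after allocation and bases it on the arm's own imaging; 5.35 gives the arms different rules. The proportion operated on is itself an outcome in 5.37, so the plan expects that it may differ between arms.

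**2. What can selection alone do?** Take two imaging profiles s with share w(s). In arm a, a share t(a,s) is operated on. Good outcome is g1(s) if operated on and g0(s) if not, the same in both arms.

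- Among operated: G(a) = Σ w·t·g1 / Σ w·t
- All randomised: A(a) = Σ w·[t·g1 + (1 − t)·g0]

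Assumed: 60% favourable and 40% unfavourable profile; control operates on 95% and 60% of them, that is 0.57 + 0.24 = 81% overall.

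If the procedure has no effect (good outcome 50% and 20% either way), A = 0.6 × 0.50 + 0.4 × 0.20 = 38.0% in both arms. Control G = (0.57 × 0.50 + 0.24 × 0.20) / 0.81 = 0.333 / 0.81 = 41.1%. If MRI operates on 85% and 20%, G = (0.51 × 0.50 + 0.08 × 0.20) / 0.59 = 0.271 / 0.59 = 45.9%, a difference of +4.8 points where the true difference is zero.

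If the procedure helps in both profiles (55% versus 30%, and 30% versus 15%), control G = (0.3135 + 0.072) / 0.81 = 47.6% and A = 0.6 × 0.5375 + 0.4 × 0.24 = 41.85%. With MRI at 85% and 20%, G = (0.2805 + 0.024) / 0.59 = 51.6% and A = 0.6 × 0.5125 + 0.4 × 0.18 = 37.95%.

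Differences, MRI minus control, in percentage points:

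| MRI operates on (favourable / unfavourable) | No effect: operated | No effect: all | Benefit: operated | Benefit: all |
|---|---|---|---|---|
| 90% / 40% | +2.0 | 0.0 | +1.7 | −1.95 |
| 85% / 20% | +4.8 | 0.0 | +4.0 | −3.9 |
| 95% / 80% | −1.9 | 0.0 | −1.6 | +1.2 |

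When the procedure helps, the sign reverses in all three rows.

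A second model gives the same order of size. It assumes logit P(good | operated) = −0.3 + 1.0 × a standard normal prognosis score, and operates on the best-ranked patients by a selection score that correlates 0.3 or 0.5 with prognosis. Operating on 50% versus 70% gives differences of 1.9 and 3.2 points; 40% versus 70% gives 2.9 and 5.0 points.

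**3. How does that compare with chance?** With 214 / 2 = 107 per arm, SE = √[p1(1 − p1)/n1 + p2(1 − p2)/n2].

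- Second model, 50% versus 70% operated: n = 53.5 and 74.9, SE about 8.9 points, and 1.9 / 8.9 = 0.2 SE.
- Second model, 40% versus 70%: n = 42.8 and 74.9, SE about 9.6 points, and 5.0 / 9.6 = 0.5 SE.
- Table, 85% / 20% with no effect: n = 63.1 and 86.7, SE about 8.2 points, and 4.8 / 8.2 = 0.6 SE. Across the table the SE runs from about 7.3 to 8.3 points.

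In the second model, Φ(−1.96 + d) + Φ(−1.96 − d), with d the shift in SE units, puts the chance of P < 0.05 through selection alone at 5.5% for the 1.9-point case and 8.2% for the 5.0-point case, instead of 5%.

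**The case against.** Four points are fairly made on the other side.

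- A reader might infer that the protocol compares good functional outcome only among operated patients. It does not. Item 6 compares 0-2 versus 3-6 without that restriction, the primary outcome includes patients treated with drugs alone, and 5.33 speaks of assessing secondary outcomes in the included study population. This stands, and confines the point to one item. It does not repair that item, which is listed separately with its own denominator.
- The line mentions no comparison or test, whereas item 6 does, so it may be meant as description. That is possible. But it stands under the secondary outcomes, and 5.34 tests secondary efficacy outcomes between groups without exception, so following the text as written produces the test.
- Outcome among those selected is relevant to the secondary objective. It is, as a description beside the proportion operated on. That does not require a between-arm P value.
- The size is assumed and small against sampling error. This also stands. Both arms use a 70 mL limit in their main criterion, and the operated shares may turn out alike. The concern is a systematic error in what the item estimates, not a large inflation of false positives.

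A further tempting reading is that the item will favour MRI. The documents do not show which rule is stricter, and the third row of the table goes the other way.

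**Conclusion.** The point holds for this one secondary outcome. Taken together, 5.33, 5.34, 5.35 and 5.37 yield an unadjusted between-arm test on a denominator that the allocated strategy creates. It is unbiased only if both strategies select patients of the same prognosis, which the protocol does not ensure. The 2 to 5 points are illustrative, rest wholly on assumed selection and outcome rates, and amount to about 0.2 to 0.6 standard errors at 107 per arm. The possible reversal of sign is likewise shown only under assumed rates. Nothing here impugns the primary outcome or item 6. It is a moderate fault, worth correcting because the item bears on the trial's central question and costs almost nothing to change.

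**What to change.** In 5.37, state that the between-arm test of good prognosis is the existing item 6 comparison, 90-day modified Rankin 0-2 versus 3-6, by allocated arm in all randomised patients. The alternative is all patients with confirmed occlusion, to match the primary population, provided occlusion is ascertained alike in both arms; this needs checking, because 5.33 provides MRA in the MRI arm and MRA or CTA in the control arm. Use the same definition of good prognosis in the operated-patient line, and report that line descriptively within each arm, without a between-arm P value, beside the proportion operated on. Add to 5.34 that this line is exempt from testing.

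The cost is a few words and a table footnote, since the data are already collected. The P value in the operated subset is given up.

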### **5. Study design**

#### **5.1 Study design**

The *MIEL* study is a multi-centre, prospective, randomized, open-label, blinded endpoint (PROBE) trial with a non-inferiority design. The study process was permitted by the ethics committee.

The study's emergency green channel team screened patients at 6-24 hours of onset for possible large vessel occlusion based on head CT scan and NIHSS score of  $\geq 6$  as the proposed cohort. Patients who met the entry criteria were then randomized 1:1 by the arriving stroke specialist into two groups 1 and 2 as follows, with the order of randomization being the responsibility of an independent investigator.

1.The MRI group performed DWI, FLAIRE, T1, T2 and MRA sequences.

2.The Control group underwent MRA or CTA, perfusion sequences, and F-stroke software (Brain Seal Smart Technology).

All patients were treated with standard Endovascular therapy and or optimal

drug therapy. The primary outcome was the overall distribution of modified Rankin scale scores at 90 days after surgery in the two groups of patients with modified intention-to-treat (**mITT**, defined as patients who had been optimally treated for acute macrovascular occlusion), as assessed by adjusted common odds ratios. Multiple secondary outcomes, including death, symptomatic intracranial hemorrhage, and ischemic regional reperfusion, were also assessed in the included study population.

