### **5.43 Endovascular Treatment Specifications**

Endovascular therapy includes mechanical embolization and balloon dilation or stenting. Thrombectomy allows the use of CFDA-approved thrombectomy devices such as stent-like devices and aspiration systems. For patients with underlying atherosclerotic stenosis after embolization, balloon dilation may be used alone, and stenting may be performed if necessary. For occluded vessels, no more than 5 thrombectomy attempts should be performed. Remedial measures after failed thrombectomy are permitted by pharmacologic arterial thrombolysis or intravenous infusion of antiplatelet agents, such as urokinase or rtPA arterial thrombolysis; rtPA is generally 1/3 of intravenous thrombolysis and can be administered intracatheterally, usually at a rate of 1 mg/min. urokinase is usually administered at a total dose of no more than 600,000 u at a rate of 1 to 20,000 U/min. Remedial therapy with balloon angioplasty or stenting is allowed. Failure to achieve a reperfusion grade of mTICI2b after remedial therapy is considered a failure of thrombus retrieval, and the case is considered a violation of the enrollment protocol, and the data can only be analyzed by mITT and cannot be included in the protocol compliance data set for PP analysis. In the case of re-occlusion at 24 hours after the procedure, it was also considered a recanalization failure and a violation of the enrollment protocol, and the data were analyzed only by mITT and not by PP.

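### Secondary outcome 2 is named as reperfusion after the procedure but is graded on the first intracranial angiogram, which read literally precedes treatment

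*Protocol*

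**What the plan says.** Section 5.37 introduces secondary outcome 2 as "Successful reperfusion after embolization, defined as an extended Thrombolysis in Cerebral Infarction (eTICI" and completes the definition with a "score of 2b, 2c or 3 at the time of the first intracranial angiogram". One sentence therefore gives the outcome a label that places it after treatment and a grading time tied to the first run.

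The other sections that bear on it are these:

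- Section 5.1 lists the outcome only in general terms: "Multiple secondary outcomes, including death, symptomatic intracranial hemorrhage, and ischemic regional reperfusion". Section 5.33 lists it in much the same way. Neither names a scale or a run.
- Section 5.35 makes vessel occlusion a condition for the procedure. For the MRI group, "MRA meets the criteria for large vessel occlusion"; for the control group, "MRA/CTA was consistent with large vessel occlusion".
- Section 5.36 makes stenting the first-choice method and adds that "if unsuccessful, suction devices may be used as a second-line option".
- Section 5.43 caps thrombectomy at five attempts and permits remedial drug, balloon or stent treatment. It treats a case as a retrieval failure if mTICI 2b is not reached once remedial therapy has been given. That rule decides exclusion from the per-protocol set and does not refer to secondary outcome 2.
- The core-laboratory paragraph after the outcomes list provides for blinded reading by two people but does not say which angiographic run they grade.

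**The concern.** A reperfusion outcome is meant to show what the procedure achieved, so the run on which it is graded is part of its definition. Here the protocol does fix a run, but one that conflicts with the outcome's name. This is not a detail left for the SAP: the time point is stated, and as stated it does not fit.

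Readers who follow the time point and readers who follow the label could grade different runs for the same patient. A patient who reaches 2b only after remedial therapy would be a non-success in 5.37 on every reading except the completion run, but not a retrieval failure under the rule in 5.43. No other listed outcome fills the gap: item 3 records vessel status by CTA at 24 to 72 hours, not the grade at the end of the procedure.

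**Working it through.** The protocol gives no figure to reproduce, so the check is a comparison of the text followed by the limits that follow from the definitions.

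**Step 1. Does any section name another run?** Every section that mentions reperfusion, revascularization, recanalization, TICI or angiography was read for this: 5.1, 5.33, 5.36, 5.37 with its core-laboratory paragraph, 5.42, 5.43 and the list of reasons for terminating endovascular therapy. None says that the completion run is graded for secondary outcome 2. The termination list asks for the time of revascularization to be recorded but names no run for grading.

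**Step 2. Does the label settle it?** It would if *embolization* had one meaning, but the protocol uses the word in several senses:

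- the whole procedure, in 5.33: "All patients were treated with the standard embolization procedure";
- one component beside others, in 5.43: "Endovascular therapy includes mechanical embolization and balloon dilation or stenting";
- a single attempt, in the termination list, which counts how often the same site was treated.

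Reperfusion after embolization could therefore mean after one attempt, after all thrombectomy passes, or after the whole procedure.

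**Step 3. The possible readings.** Let S be the number of patients whose vessel reaches 2b or better through the procedure. The uncounted share is the part of S that first reaches 2b after the graded run.

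| Reading | Run graded | Uncounted share of S |
|---|---|---|
| 1 (literal) | Before any device pass | S/S = 100% |
| 2 | First run after the first pass | (first reach 2b on attempts 2 to 5, with the second-line device, or after remedial therapy)/S; not derivable |
| 3 | First run after all thrombectomy passes | (first reach 2b after remedial therapy)/S; not derivable |
| 4 | Completion run after all treatment | 0/S = 0% |

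The patients missed under reading 3 are a subset of those missed under reading 2, so the order is 0% ≤ reading 3 ≤ reading 2 ≤ 100%.

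Under reading 2, the cap of five in 5.43 leaves 5 − 1 = 4 permitted attempts after the graded run, plus any remedial therapy. Four is a maximum, because the other termination rules may end treatment sooner. It counts permitted attempts, not patients.

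**Step 4. Check on reading 1.** A run made before any device is used cannot show reperfusion produced by a device. The only successes it could record are vessels already open at that run. The occlusion criteria in 5.35 make these unlikely to be the intended target, and the termination list gives spontaneous recanalization as a reason to end endovascular therapy.

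**Step 5. Comparison with 5.43.** Take a patient below 2b after every pass who reaches 2b after remedial therapy. Under 5.43 this is not a failure to reach the required grade. Under 5.37 it is a non-success on readings 1, 2 and 3, and a success only on reading 4.

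**The case against.** The strongest reply is that the definition is one sentence and should be read whole. It opens by placing the outcome after the procedure, so the first angiogram would naturally be the first one after that event. The text also reads like a translation, so a single word should not carry too much weight. On this view the fault is an under-specified post-treatment run, not a contradiction. That is a fair reading of what was probably intended, but it does not rescue the definition: a first run after treatment may still be reading 2 or 3, and the protocol does not choose.

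Other objections stand in part:

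- The rule in 5.43 serves the per-protocol set, and two rules with two purposes may use different time points. That is correct, so the difference is not an error in itself. It does show that the protocol already treats status after remedial therapy as the measure of procedural success.
- Imaging goes to a separate core laboratory, which could apply one convention to both arms, and no bias between arms is shown. This makes divergent grading a possibility rather than a demonstrated fact. The convention still has to be written down, and the only one written is the first run.
- The occlusion requirement in 5.35 is not absolute, since operator experience may decide where MRI has failed. This does not matter for reading 1, which follows from the run being made before any device is used.
- Choosing the completion run goes beyond what the text strictly dictates. That is so; it is recommended because it is the only reading that leaves out no reperfusion achieved by the procedure.

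**Conclusion.** The time point of secondary outcome 2 is wrong as written. Followed literally, it grades flow before treatment under a label that promises flow after treatment. On the softer readings short of the completion run, it omits reperfusion gained on later attempts or by remedial therapy. No other section corrects it.

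The practical size is unknown, because the protocol gives no reperfusion or rescue rates and none is assumed here. Only the limits are firm: 100% of procedure-achieved reperfusions uncounted on the literal reading, and 0% on the completion-run reading. The literal limit rests on taking the first intracranial angiogram to be the run made before any device pass.

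The consequence is confined to one secondary outcome, relevant only to patients who receive endovascular treatment. The primary 90-day mRS analysis is unaffected. It should be corrected, but it does not threaten the trial's main conclusion. The use of eTICI in 5.37 and mTICI in 5.43 is a minor inconsistency; no patient is shown to be misclassified by the scale alone.

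**What to change.** In 5.37, item 2, replace the reference to the first angiogram with: *on the final angiogram at the end of the procedure, including any remedial therapy*. If a first-run or first-pass grade is also wanted, list it as a separate, named outcome. Use one reperfusion scale in 5.37 and 5.43.

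The cost is one line of wording, plus the alignment of the scale. Section 5.43 already requires a reperfusion judgement after remedial therapy, so the change should call for no additional angiography. The protocol does not say that this judgement is a core-laboratory eTICI reading, so the core laboratory's instructions should state that the final run is the one graded, on the chosen scale, in every patient who undergoes the procedure. The change defines a measurement and does not alter how patients are treated.
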